6.2.2 Enrollment, Baseline, and/or Randomization

Enrollment

This study will occur at a single site, the University of Michigan. If a subject expresses interest in the study and completes the informed consent process, their eligibility based on the full inclusion/exclusion criteria will be verified during the screening visit. Study personnel will follow up with the subject after consent to schedule all research visits. The subject will be deemed enrolled upon meeting the study eligibility criteria.

Baseline Assessments

If patients meet eligibility criteria, we will ask them (during the screening visit) if they would like to enroll in the study. If they enroll, we will ask them to sign an informed consent form/document, and invite them to be part of various study visits. During the baseline at Visit 1, the following assessments will be performed:

- Assess patients' psychological status (e.g., anxiety, depression) using self-reported patient questionnaires/surveys (e.g., EuroQol questionnaire, EQ-5D⁵ and Hospital Anxiety and Depression Scale, HADS).⁶⁰
 - If patients meet criteria for extreme anxiousness or depression (as indicated in the EQ-5D questionnaire or an equivalent score of 11-21 on HADS) we will offer/provide them with a "Depression Resource Handout". However, patients can still continue their participation in the study.
- Collect patients' vital signs (heart rate, blood pressure, respiration rate, and body temperature), height, and weight.
- Collect demographics, sociodemographics, and concomitant medications from the patients.

Randomization

Within two months of enrollment, we will randomize subjects to one of six randomly allocated sequences consisting of the following treatments: burst, 1 kHz, sham, and 50Hz SCS. Subjects will receive each treatment for seven days following one of the six randomly allocated

sequences (crossover design) (Fig. 3.1). We will perform testing before the start of the randomization and at the end of each seven-day treatment period. Subjects will be blinded during programming. To ensure proper blinding, we will set the amplitude of stimulation so that patients do not feel any stimulation-induced paresthesias (except for 50 Hz SCS which requires paresthesias).² Sham SCS will be performed by setting the amplitude to 0 mA.² For some systems, if the stimulation amplitude is decreased to 0 mA, the system will report that the stimulation is OFF and the participants will know that they are not receiving stimulation. Therefore, for these systems, we will perform sham SCS by setting the stimulation parameters to their minimal values: pulse width (~20 μ s), frequency (~2 Hz), and amplitude (~0.1 mA).

6.2.3 Blinding

We will have two research teams. One team will be unblinded and will perform stimulator programming/adjustment, and the other team will be blinded and will perform clinical testing and collect study outcome measures.

Participants will be blinded during programming. During the stimulator programming session, we will adjust the settings on the subjects' SCS device. We will adjust the settings such that subjects will receive seven days of a specific treatment allocation. To ensure proper blinding during the first three treatment allocations, we will set the stimulation amplitude so that the participants do not feel any stimulation-induced paresthesias. Sham SCS will be performed by setting the amplitude to 0 mA. For some systems, if the stimulation amplitude is decreased to 0 mA, the system will report that the stimulation is OFF and the participants will know that they are not receiving stimulation. For these systems, we will perform sham SCS by setting the stimulation parameters to their minimal values: pulse width (~20 μ s), frequency (~2 Hz), and amplitude (~0.1 mA). Therefore, participants will not experience stimulation-induced paresthesias during Sham SCS. However, during an active treatment allocation, stimulation-induced paresthesias may sometimes occur (usually as a tingling sensation) due to positional changes (e.g., bending, lifting) and/or extreme movement. To minimize the occurrence of these stimulation-induced paresthesias, we will have the participants assume multiple positions (e.g., sitting, standing, supine, prone) during the programming session and ensure that the stimulation amplitude is low enough to avoid stimulation-induced paresthesias in any of these bodily positions. Therefore, the participant experience should be similar for the first three treatments. After completion of the first three treatment allocations, each participant will receive seven days of tonic 50 Hz SCS that will generate paresthesias over their painful areas. While having 50 Hz SCS as the last treatment in all participants may introduce a potential order effect, this treatment is performed last because patients will likely know that they are receiving active stimulation due to the paresthesias and this design will minimize the chance of breaking the blind during the first three treatment allocations.

During this study, it is possible that participants may experience insufficient pain relief and/or discomfort during some of the treatments. Therefore, to reduce patient risk we will allow patients to keep the patient programmer. The participants will be instructed not to adjust the stimulation settings during each treatment. At the end of each treatment allocation, we will interrogate the participant's implanted stimulator to ensure that the stimulation settings were not altered during the specific treatment phase. For some systems, patients are given a magnet that can be used to turn the stimulation off in the case of an emergency. For participants with these systems, we will instruct the participants to use the magnet, if needed, in the case of emergency. The magnet can be used to turn the stimulation on or off, in the absence of the programmer.

It is possible that during some treatment allocations, such as during Sham SCS, participants may experience insufficient pain relief. If participants complain of significant discomfort and they are considering exiting the study, we will have the unblinded study

personnel examine the current treatment allocation to determine if the participant is receiving stimulation settings that vary substantially from their clinical parameters. If necessary, the participant can decide to have the stimulation settings returned to those determined to be effective through standard-of-care programming procedures.

6.2.4 Followup Visits

- Visit 3 (*Day 7 \pm 2 days*):
 - Vital signs
 - Concomitant medications
 - Surveys and questionnaires
 - Quantitative sensory testing
 - Administer treatment
 - Stimulator programming
 - Adverse events
- Visit 4 (*Day 14 \pm 2 days*):
 - Vital Signs
 - Concomitant medications
 - Surveys and questionnaires
 - Quantitative sensory testing
 - Administer treatment
 - Stimulator programming
 - Adverse Events
- Visit 5 (*Day 21 \pm 2 days*):
 - Vital Signs
 - Concomitant medications
 - Surveys and questionnaires
 - Quantitative sensory testing
 - Administer treatment
 - Stimulator programming
 - Adverse Events

6.2.5 Completion/Final Evaluation

The following procedures will be performed during the final visit (*Visit 6 – Day 28 \pm 2 days*):

- Vital Signs
- Concomitant medications

- Surveys and questionnaires
- Quantitative sensory testing
- Stimulator programming
- Adverse Events
- Study debriefing

After the completion of all study procedures, the participants stimulation parameters will be returned to the settings selected through standard-of-care programming procedures.

As detailed in Section 8, there are many reasons for participants to discontinue the study early. Subject participation is strictly voluntary and the research strictly knowledge driven; therefore, a subject may withdraw from further participation in the study without penalty or harm. Any reason(s) the subject may give for terminating his or her participation will be kept confidential. We will store the study documents according to the procedures outlined in the Section 11.3 of this protocol. Study personnel will be authorized to release a subject from further study participation according to the following guidelines:

- The researcher believes that it is not in the subject's best interest to stay in the study.
- Subject becomes ineligible to participate.
- Subject's condition changes such that they need treatment that is not allowed while taking part in the study.
- Subject does not follow instructions from the researchers.
- The study is suspended or canceled.

Upon termination of a subject, the investigators will ensure the subject is dismissed with any study documents to which they are entitled. Subjects will be compensated for their completed study visits prior to termination. Investigators will require no further obligation or participation from a terminated subject. The reason for participant discontinuation or withdrawal from the study will be recorded on the appropriate Case Report Form (CRF).

Discontinuation from SCS will require discontinuation from the study, and remaining study procedures will not be completed. If a clinically significant finding is identified (including, but not limited to changes from baseline) after enrollment, the investigator or qualified designee will determine if any change in participant management is needed. Any new clinically relevant finding will be reported as an adverse event (AE).

7. SAFETY ASSESSMENTS

7.1 Specification of Safety Parameters

Participant safety will be monitored while individuals are enrolled in the study. The table below lists expected risks by study intervention/procedure, as well as criteria for management and modification of the study intervention regimen or participant assessments if an adverse event occurs.

Known Potential Risks	Criteria for Management	Intervention Modification (if any)
Electrical stimulation	
 • Muscle contractions • Shock hazard (i.e., electrical burn) • Participant complains of 	
 • Stimulation amplitude will first be set to a low amplitude. • We will only use stimulators approved by the U.S. Food

	discomfort	and Drug Administration.
Medical Imaging procedures (CT)	
 • Exposure to radiation and increased risk of cancer • Participant may experience discomfort or anxiety from being in the confined space • Claustrophobia 	
 • Participant consent form will identify the cumulative risks of radiation and exposure. • Pads and blankets will be provided to reduce discomfort.
Quantitative Sensory Testing (QST)	
 • May cause minor but temporary physical discomfort 	
 • Study personnel are trained by the investigator to be sensitive to participant discomfort and concerns. • Participants are able to stop the QST at any time.
Multimodal Automated Sensory Testing (MAST)	
 • Participant complains of physical discomfort on the thumbnail 	
 • Participants will always have personal control over the stimulus and can stop it at any time or express instructions to stop. • Participants can withdraw their thumb from the device or turn a safety release pin to immediately release the pressure actuator.
The Vibrometer, Pressure Algometer, Pointed Skin Probe, and Conditioned Pain Modulation (CPM) Test	
 • Participant complains of discomfort in the areas of testing • Skin irritation/redness 	
 • The test can be halted if the participant reports a pain rating of 100. • The participant can inform study personnel to stop the test at any time that the pain or unpleasantness of the task becomes intolerable.

7.2 Methods and Timing for Assessing, Recording, and Analyzing Safety Parameters

Study progress and safety will be reviewed monthly (and more frequently if needed). Progress reports, including patient recruitment, retention/attrition, and adverse events (AEs) will be provided to the Independent Monitoring Committee (IMC) semi-annually. An Annual Report will be compiled and will include a list and summary of AEs. In addition, the Annual Report will address (1) whether AE rates are consistent with pre-study assumptions; (2) reasons for dropouts from the study; (3) whether all participants met entry criteria; (4) whether continuation of the study is justified on the basis that additional data are needed to accomplish the stated aims of the study; and (5) conditions whereby the study might be terminated prematurely. The Annual Report will be sent to the IMC and will be forwarded to the Institutional Review Board

(IRB) and National Center for Complementary and Integrative Health (NCCIH). The IRB and other applicable recipients will review progress of this study on an annual basis.

7.3 Adverse Events and Serious Adverse Events

Adverse event (AE) means any untoward medical occurrence associated with the use of an intervention in humans, whether or not considered intervention-related (21 CFR 312.32 (a)). An AE or suspected adverse reaction will be considered "serious" if, in the view of either the investigator or sponsor, it is any AE that:

- Is fatal;
- Is life threatening, meaning the patient was at immediate risk of death from the reaction as it occurred, i.e., it does not include a reaction that, had it occurred in a more serious form or progressed, might have caused death;
- Causes a persistent or significant disability or incapacity;
- Requires or prolongs inpatient hospitalization. Inpatient hospitalization will be considered a hospitalization if it is longer than 24 hours or requires an intervention to treat emergent symptomatology (non-diagnostic);

Other important medical events may be considered SAEs when, based upon appropriate medical judgment, they may jeopardize the patient and may require medical or surgical intervention to prevent one of the outcomes as listed in this definition. We will report SAEs to the IRBMED per the IRBMED Standard AE Reporting Plan at <https://az.research.umich.edu/file/864>. If the SAEs are not related to the study, we will report them at Continuing Review. If the SAEs are related to the study, we will report them within seven days or sooner to the IRB. We will also report AEs and SAE's to the Principal Investigator (PI). If there is any evidence of a pattern of unanticipated AEs (regardless of causality), or SAEs, we will immediately have an independent third party review these data. Based on the conclusions of this third party, the PI will either terminate the study or convene the Data Safety and Monitoring Board (DSMB) to make recommendations.

7.4 Reporting Procedures

Severity of event: We will grade the signs and symptoms as mild, moderate, severe, or life threatening according to the following definitions:

Grade	Definition
Mild	Causing no limitation of usual activity
Moderate	Causing some limitations of usual activities
Severe	Causing inability to carry out usual activities
Life Threatening	Patient was at immediate risk of death from the event

Relationship to study intervention: All adverse events (AEs) must have their relationship to study intervention assessed by the clinician who examines and evaluates the participant based on temporal relationship and his/her clinical judgment. The degree of certainty about causality will be graded using the categories below.

- **Related** – The AE is known to occur with the study intervention, there is a reasonable possibility that the study intervention caused the AE, or there is a temporal relationship

between the study intervention and event. Reasonable possibility means that there is evidence to suggest a causal relationship between the study intervention and the AE.

- **Not Related** – There is not a reasonable possibility that the administration of the study intervention caused the event, there is no temporal relationship between the study intervention and event onset, or an alternate etiology has been established.

Expectedness: The study Principal Investigator (PI) will be responsible for determining whether an adverse event (AE) is expected or unexpected. An AE will be considered unexpected if the nature, severity, or frequency of the event is not consistent with the risk information previously described for the study intervention.

Time period and frequency for event assessment and follow-up: The occurrence of an adverse event (AE) or serious adverse event (SAE) may come to the attention of study personnel during study visits and interviews of a study participant presenting for medical care, or upon review by a study monitor.

All AEs including local and systemic reactions not meeting the criteria for SAEs will be captured on the appropriate case report form (CRF). Information to be collected includes event description, time of onset, clinician's assessment of severity, relationship to study product (assessed only by those with the training and authority to make a diagnosis), and time of resolution/stabilization of the event. All AEs occurring while on study will be documented appropriately regardless of relationship. All AEs will be followed to adequate resolution.

Any medical condition that is present at the time that the participant is screened will be considered as baseline and not reported as an AE. However, if the study participant's condition deteriorates at any time during the study, it will be recorded as an AE.

Changes in the severity of an AE will be documented to allow an assessment of the duration of the event at each level of severity to be performed. AEs characterized as intermittent require documentation of onset and duration of each episode.

Reporting adverse events: We will report SAEs to the IRBMED per the IRBMED Standard AE Reporting Plan at <https://az.research.umich.edu/file/864>. If the SAEs are not related to the study, we will report them at the study continuing review. If the SAEs are related to the study, we will report them within seven days or sooner to the IRB. We will also report AEs and SAEs to the Principal Investigator (PI). If there is any evidence of a pattern of unanticipated AEs (regardless of causality), or SAE, we will immediately have an independent third party review these data. Based on the conclusions of this third party, the PI will either terminate the study or convene a Data Safety and Monitoring Board (DSMB) to make recommendations.

Reporting events to participants: We will inform both the subject and the subject's physician in the event that a potentially significant, unexpected disease or condition is identified incidental to a study treatment or procedure.

Reporting of pregnancy: As part of this research, participants may undergo specific medical imaging procedures, such as X-ray computed tomography (CT). For this research, we will consider pregnancy a contraindication for these medical imaging procedures. Therefore, before performing any medical imaging procedure as part of this research, we will perform a urine pregnancy tests for participants of child bearing potential, and having no intrauterine device (IUD) or hysterectomy, and who are able to become pregnant. If a participant becomes pregnant or nursing after enrollment and/or does not wish to take the pregnancy test at the screening visit, the participant will be excluded from the imaging procedures but will be allowed to remain in the study and participate in the remaining study procedures. This information will be

reported to the IRB as an Other Reportable Information or Occurrences (ORIO) within seven calendar days of becoming aware of the event or information.

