6. STUDY PROCEDURES

6.1 Schedule of Evaluations

	Screening/ enrollment visit	Randomization ^a	Treatment	Treatment	Treatment (50 Hz SCS)	Final visit
	Visit 1 Day -62 to Day 0	Visit 2 Day 0 ± 2 days	Visit 3 Day 7 ± 2 days	Visit 4 Day 14 ± 2 days	Visit 5 Day 21 ± 2 days	Visit 6 Day 28 ± 2 days
Informed Consent	X					
Hospital Anxiety and Depression Scale (HADS)	X	X	X	X	X	X
EQ-5D Health Questionnaire	X	X	X	X	X	X
Demographics	X					
Concomitant Medications	X	X	X	X	X	X
Socio-demographics	X					
Urine Pregnancy Test	X					
Brief Pain Inventory (BPI)	X	X	X	X	X	X
Coping Strategies Questionnaire (CSQ)	X	X	X	X	X	X
Michigan Body Map (MBM)	X	X	X	X	X	X
PainDETECT	X	X	X	X	X	X
Pain Disability Index (PDI)	X	X	X	X	X	X
Fibromyalgia Survey Questionnaire (FSQ)	X	X	X	X	X	X
Patient-Reported Outcomes Measurement Information System Sleep Disturbance Short Form Questionnaire (PROMIS-SD)	X	X	X	X	X	X
Short Form McGill Pain Questionnaire (SFMPQ)	X	X	X	X	X	X
Visual Analog Scale (VAS) – included in SFMPQ	X	X	X	X	X	X
Vitals (heart rate, blood pressure, respiration rate, blood temperature), height and weight	X	X	X	X	X	X
Multimodal Automated Sensory Test (MAST)	b	X	X	X	X	X
Vibrometer Test	b	X	X	X	X	X
Algometer Test	b	X	X	X	X	X
Temporal summation (TS) – PinPrick Test	b	X	X	X	X	X
Conditioned Pain Modulation (CPM) Test	b	X	X	X	X	X
Computed tomography (CT)		X				
Randomization		c				
Treatment (Burst, 1kHz, 50Hz, Sham SCS)		d	X	X	X	X

Stimulator programming		X	X	X	X	X
Adverse Events	X	X	X	X	X	X
Study debriefing						X

^a *The randomization visit (Visit 2) may also occur on the same day as the screening/enrollment visit (Visit 1)*

^b *Familiarization only*

^c *Randomization will occur at the end of Visit 2*

^d *Treatment will begin at the end of Visit 2*

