6.2 Description of Evaluations

The schedule of study procedures and assessments is 6.1 Schedule of Evaluations. The descriptions of the procedures to be performed at each visit are provided below.

Screening/enrollment (Visit 1)

- Review study procedures and requirements with participant
- Review informed consent, only for candidates that do not consent electronically via SignNow.
- Collect demographic and sociodemographic information
- Conduct psychological screening assessment (HADS)
- Collect vital signs (heart rate, blood pressure, respiration rate, body temperature, height and weight)
- Obtain medical history (EQ-5D Health Questionnaire) and FM Survey Questionnaire [FSQ]
- Collect symptoms of chronic pain
 - Pain disability Index (PDI)
 - Short Form McGill Pain Questionnaire (SFMPQ)
 - Michigan Body Map (MBM)
 - PainDETECT
 - Brief Pain Inventory (BPI)
 - Visual Analog Scale (VAS) and SFMPQ
- Determine impact of chronic pain on daily life (CSQ)
- Administering a urine pregnancy test to women of childbearing potential
- Document current concomitant medications
- Familiarize participant to the sensory testing procedure
 - Multimodal Automated Sensory Test (MAST)
 - Vibrometer Test
 - Algometer Test
 - PinPrick Test
 - Conditioned Pain Modulation (CPM) Test
- Documentation of any adverse events

Randomization (Visit 2)

After a participant has been deemed a candidate for the study, this visit can occur on the same day as Visit 1 (screening/enrollment).

- Collect vital signs (heart rate, blood pressure, respiration rate, body temperature, height and weight)
- Review and record any changes in concomitant medications
- Rate participants current pain on a scale Visual Analog Scale (VAS) and SFMPQ
- Collect
 - Pain disability Index (PDI)
 - Short Form McGill Pain Questionnaire (SFMPQ)
 - Michigan Body Map (MBM)
 - PainDETECT
 - Brief Pain Inventory [BPI]
 - Visual Analog Scale (VAS) and SFMPQ
 - Coping Strategies Questionnaire (CSQ)
 - Hospital Anxiety and Depression Scale (HADS)

- EQ-5D Health Questionnaire
 - Fibromyalgia Survey Questionnaire (FSQ)
- Conditioned Pain Modulation (CPM) Test – Assessment to examine how the body naturally controls pain
- Measure participant's sensitivity to different stimuli
 - Vibrometer Test
 - Algometer Test
 - PinPrick Test (Temporal summation)
 - Multimodal Automated Sensory Test (MAST)
- Randomization*
- Deliver treatment (Burst, 1kHz, or Sham SCS)
- Stimulator programming
 - Perception threshold

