 - Discomfort threshold
 - Paresthesia mapping
- Documentation of any adverse events
- Computed tomography (CT) scan

*At the end of the Visit 2, randomization will occur. We will randomize participants to one of six randomly allocated sequences that each contain four treatments: burst, 1 kHz, sham, and 50 Hz SCS. Participants will receive each treatment for seven days.

Treatment (Visit 3)

After participants have received approximately seven days of the first treatment, we will perform the study procedures listed below. After performing these study procedures, the stimulation parameters will be adjusted to apply the second treatment allocation in the respective treatment arm. Participants will be blinded during programming.

- Collect vital signs (heart rate, blood pressure, respiration rate, body temperature, height and weight)
- Review and record any changes in concomitant medications
- Rate participants current pain on a scale Visual Analog Scale (VAS) and SFMPQ
- Collect
 - Pain disability Index (PDI)
 - Short Form McGill Pain Questionnaire (SFMPQ)
 - Michigan Body Map (MBM)
 - PainDETECT
 - Brief Pain Inventory [BPI]
 - Visual Analog Scale (VAS) and SFMPQ
 - Coping Strategies Questionnaire (CSQ)
 - Hospital Anxiety and Depression Scale (HADS)
 - EQ-5D Health Questionnaire
 - Fibromyalgia Survey Questionnaire (FSQ)
- Conditioned Pain Modulation (CPM) Test – Assessment to examine how the body naturally controls pain
- Measure participant's sensitivity to different stimuli
 - Vibrometer Test
 - Algometer Test
 - PinPrick Test (Temporal summation)
 - Multimodal Automated Sensory Test (MAST)
- Deliver treatment (Burst, 1kHz, or Sham SCS)

- Stimulator programming
 - Perception threshold
 - Discomfort threshold
 - Paresthesia mapping
- Documentation of any adverse events

Treatment (Visit 4)

After participants have received approximately seven days of the second treatment, we will perform the study procedures listed below. After performing these study procedures, the stimulation parameters will be adjusted to apply the third treatment allocation in the respective treatment arm. Participants will be blinded during programming.

- Collect vital signs (heart rate, blood pressure, respiration rate, body temperature, height and weight)
- Review and record any changes in concomitant medications
- Rate participants current pain on a scale Visual Analog Scale (VAS) and SFMPQ
- Collect
 - Pain disability Index (PDI)

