- Conducting a physical assessment (height and weight) and collecting vital signs
- Completing and reviewing Psychological Screening questionnaires (HADS)
- Administering a urine pregnancy test to women of childbearing potential
- Documenting and reviewing current concomitant medications

Completion of these screening procedures will allow the study personnel to verify that the subject meets the full inclusion/exclusion criteria. For this study utilizing a single consent form, randomization should occur within two months of completing the screening procedures.

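### The only scheduled pregnancy test can precede the research CT by about two months, and no repeat is scheduled before the scan

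*Combined protocol and SAP*

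**What the plan says.** Section 7.4 (Reporting of pregnancy) makes pregnancy a contraindication to the study's imaging. It then says that "before performing any medical imaging procedure as part of this research, we will perform a urine pregnancy tests" for participants of childbearing potential who have no IUD or hysterectomy and are able to become pregnant. Its next sentence says that a participant who becomes pregnant or nursing after enrollment, or who declines the test at the screening visit, has no imaging but may stay in the study. This is reported to the IRB within seven calendar days.

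Section 6.1 marks the row "Urine Pregnancy Test" once, at Visit 1 (Day -62 to Day 0), and marks the CT once, at Visit 2 (Day 0 ± 2 days). Note a says that the randomization visit "may also occur on the same day as the screening/enrollment visit (Visit 1"; note c says "Randomization will occur at the end of Visit 2".

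In Section 6.2, "Administering a urine pregnancy test to women of childbearing potential" appears under Visit 1 and "Computed tomography (CT) scan" under Visit 2. The Visit 2 list has no pregnancy test or pregnancy question. Section 6.2.1 again lists the test as a screening procedure and adds that "randomization should occur within two months of completing the screening procedures". Section 6.2.2 says "Within two months of enrollment, we will randomize subjects", with enrollment dated from meeting the eligibility criteria.

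Section 2.2 describes the CT as outside standard clinical care and as adding radiation exposure.

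**The concern.** The pregnancy test has a stated purpose: to keep a pregnant participant from being scanned. A result up to two months old cannot serve that purpose. Section 7.4 also bars imaging for anyone who becomes pregnant after enrollment, yet no scheduled step between Visit 1 and the CT would detect such a pregnancy. Visit 2 includes adverse-event documentation and a medication review, and Section 7.5 has the investigator ask about adverse events at each visit. These could bring out a pregnancy the participant knows about, but not one she does not.

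At stake is avoidable radiation exposure during an unrecognized pregnancy, from a scan done only for research. Sections 4 and 4.2 state that the research will not involve pregnant women or fetuses. This is a participant-safety point and has no bearing on the temporal summation analysis.

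**Working it through.** **Inputs**

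| Item | Value | Source |
|---|---|---|
| Pregnancy test | Visit 1 only, Day -62 to Day 0 | 6.1; also 6.2 and 6.2.1 |
| CT | Visit 2 only, Day 0 ± 2 days | 6.1; also 6.2 |
| Same-day Visits 1 and 2 | Allowed, not required | 6.1 note a; 6.2 |
| Screening to randomization | Within two months, worded as *should* | 6.2.1 |
| Expected women | 15 of 25, a target only | 4 |

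**Interval from test to scan** = day of CT − day of test.

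- Shortest: 0 days, when the visits share a day.
- Longest at the nominal visit days: 0 − (−62) = 62 days.
- Longest with the Visit 2 window: 2 − (−62) = 64 days.
- Check against the text: two consecutive calendar months span 31 + 28 = 59 to 31 + 31 = 62 days, which agrees with Day -62.

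Because Section 6.2.1 says only that randomization should occur within two months, these figures describe the planned window and are not a strict cap.

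**Scheduled tests.** There is one in total, at Visit 1. When Visit 2 falls on a later day, none is scheduled at or just before the scan.

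**Does Section 7.4 close the gap?** It requires a test before imaging but gives no interval, and the only test it goes on to mention is the one at screening. A negative Visit 1 result satisfies the word *before*. Section 7.4 and the Schedule therefore do not contradict each other; what is missing is the timing.

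**Number of extra tests under the fix.** At the targeted split, 25 × 15/25 = 15, assuming that every woman is able to become pregnant, is to have the CT and has the two visits on different days. If all 25 randomized participants were such women, the number would be 25. A few more are possible, because the test would precede randomization at the end of Visit 2 and because Section 8 allows some randomized subjects to be replaced.

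The real number is probably lower than 15 at the targeted split. Participants with an IUD or hysterectomy, those unable to become pregnant, those who declined the screening test (no imaging under Section 7.4), those without suitable preoperative imaging (no CT under Section 9.5.2) and those with same-day visits all drop out of the count. The documents give no age distribution and no expected share of same-day visits, so the count cannot be narrowed further.

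**After the fix**, the longest scheduled interval falls from 62 days (64 with the window) to 0 days.

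**The case against.** The strongest reply is that the Section 7.4 rule is triggered by the imaging, not by screening, so staff could already test on the day of the scan. On this reading, the mention of the screening-visit test belongs to a clause about refusals and does not say that it is the only test. That reading is possible, but nothing in the Schedule or the Visit 2 list carries it out. If a scan-day test is intended, the Schedule omits it, and the text needs correcting either way.

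A second reply is that the Section 6.2 lists are incomplete. The PROMIS sleep form is scheduled at every visit but appears in none of the lists, and HADS and EQ-5D are missing from the lists for Visits 4 to 6. This is correct, and it weakens the Visit 2 list as evidence taken alone. The Schedule, the Visit 1 list and Section 6.2.1 still agree on a single test at screening.

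Third, same-day visits are expressly allowed and bring the interval to zero. That is correct, but they are optional, and the documents do not say how often they will occur.

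Fourth, the Manual of Operations mentioned in Section 10.3.1 may require scan-day checks. It may, but it cannot be seen here, and the protocol itself sets no such requirement.

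Finally, the practical consequence is not quantified: the scan is thoracic or cervical, few participants may be affected, and no exposure figure is given. This limits the weight of the point. It does not remove it, because Section 7.4 makes no exception by body region.

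**Conclusion.** The concern holds, with high confidence on the scheduling facts. As written, the plan allows the research CT up to 62 days after the only scheduled pregnancy test (64 with the visit window), and no scheduled step detects an unrecognized pregnancy in between. This rests on Visits 1 and 2 falling on separate days and on staff following the Schedule without an unseen scan-day procedure. The number of participants exposed to the gap is small and cannot be estimated from the documents. The sponsor should correct it: the protocol's own safety rule is not supported by its schedule, and the remedy is inexpensive.

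**What to change.** Add a urine pregnancy test to the Visit 2 column of Section 6.1 and to the Visit 2 list in Section 6.2, done on the day of the scan and before the CT. It applies to participants able to become pregnant (no IUD or hysterectomy) who are to have the CT. A footnote should waive it when the Visit 1 test was done the same day.

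State this timing in Section 7.4, with the handling of each result:

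1. A positive test at screening remains an exclusion under Section 4.2, including when Visits 1 and 2 share a day.
2. A positive test at a later Visit 2, after a negative screening test, means no CT. The participant stays in the study and an ORIO report is made within seven calendar days, as Section 7.4 already provides for pregnancy after enrollment.
3. A test declined at Visit 2 is handled as in item 2. This is new, because Section 7.4 covers refusal only at the screening visit.

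Items 1 and 2 restate existing rules. They are worth writing out because the new test falls after enrollment but before randomization.

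The cost is one Schedule cell with a footnote, one line in the Visit 2 list and a few sentences in Section 7.4. As a protocol amendment it needs IRB approval before use (Section 11.1), with a check on whether the consent form must change. The burden is one more urine test, of a kind the study already uses, for about 15 participants or fewer at the targeted sex split.
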